6.4 Treatment blinding

Participants, investigator and site staff, persons performing the assessments, and monitors will remain masked to the identity of the treatment from the time of randomization until database lock, using the following methods: (1) Randomization data are kept strictly confidential until the time of unmasked and will not be accessible by anyone else involved in the study (2) the identity of the treatments will be concealed by the use of study treatment that are all identical in packaging, labeling, schedule of administration and appearance.

Unmasking will occur in the case of participant emergencies and at the conclusion of the study.

Table 6-4 Masked and unmasked plan

Role	Time or Event			
	Randomization list generated	Treatment allocation & dosing	Safety event (single participant unblinded)	Interim Analysis
Participants	M	M	M	M
Site staff	M	M	M*	M
Global Clinical Supply and Randomization Office	M	M	M	M
Unmasked sponsor staff e.g. for study treatment re-supply, unmasked monitor(s), sample analyst(s)	M	UI	UI	UI
Unmasked Pharmacovigilance sponsor staff	M	M	UI	M
Statistician/statistical programmer/ data analysts	M	M	M	UI
All other sponsor staff not identified above	M	M	M	M
Key: UI: Allowed to be unmasked on individual participant level M: Remains masked *Investigator will be unmasked in case of emergency breaking of treatment code (Section 6.6.2)				

6.5 Dose escalation and dose modification

Investigational or other study treatment dose adjustments and/or interruptions are not permitted.

For participants who do not tolerate the protocol-specified dosing regimen, study treatment should be discontinued and, if possible, the subject is continued to be monitored in the study ([Section 9.1.1](#)).

6.6 Additional treatment guidance

6.6.1 Treatment compliance

Participants will be instructed at each on-therapy study visit to take the study treatment exactly as prescribed.

[figure not shown]
The investigator must promote compliance by instructing the subject to take the study treatment exactly as prescribed and by stating that compliance is necessary for the subject's safety and the validity of the study. The subject must also be instructed to contact the investigator if he/she is unable for any reason to take the study treatment as prescribed. Participants will be provided with an ed diary to complete every day after they administer study drug. Compliance will be assessed by the investigator and/or study personnel at each visit. Participants will also be instructed to bring used/unused medication bottles to the study visits and the site staff will check compliance based on the number of bottles used and ed diary data. All study treatment dispensed and returned must be recorded in the Drug Accountability Log.

6.6.2 Emergency breaking of assigned treatment code

Emergency code breaks must only be undertaken when it is required to in order to treat the participant safely. Masked codes may also be broken after a participant discontinues treatment due to disease progression if deemed essential to allow the investigator to select the participant's next treatment regimen, and after discussion and agreement with the sponsor. Most often, study treatment discontinuation and knowledge of the possible treatment assignments are sufficient to treat a study participant who presents with an emergency condition. However, participants can continue to participate in the study ([Section 9.1.1](#)). Emergency treatment code breaks are performed using the IRT. When the investigator contacts the system to break a treatment code for a participant, he/she must provide the requested participant identifying information and confirm the necessity to break the treatment code for the participant. The investigator will then receive details of the investigational drug treatment for the specified participant and a fax or email confirming this information. The system will automatically inform the Novartis monitor for the site and the study team that the code has been broken.

It is the investigator's responsibility to ensure that there is a dependable procedure in place to allow access to the IRT/code break cards at any time in case of emergency. The investigator will provide:

- protocol number
- participant number

In addition, oral and written information to the participant must be provided on how to contact his/her backup in cases of emergency, or when he/she is unavailable, to ensure that unmasking can be performed at any time.

6.7 Preparation and dispensation

Each study site will be supplied with study drug in packaging as described under investigational and control drugs section.

A unique medication number is printed on the study medication label.

Investigator staff will identify the study medication kits to dispense to the participant by contacting the IRT and obtaining the medication number(s). The study medication has a 2-part label (base plus tear-off label), immediately before dispensing the medication kit to the participant, site personnel will detach the outer part of the label from the packaging and affix it to the source document. Study medication will be dispensed to the patient at the clinic as outlined in table of assessments in [Section 8](#). In the event of COVID-19 pandemic it may be necessary to make alternative arrangements (e.g., curb-side pickup or home delivery) for the participant to obtain study medication at the designated study visit as allowed by local regulations, site capabilities and participant's comfort level.

6.7.1 Handling of study treatment and additional treatment

6.7.1.1 Handling of study treatment

[figure not shown]
Study treatment must be received by a designated person at the study site, handled and stored safely and properly and kept in a secured location to which only the investigator and designated site personnel have access. Upon receipt, all study treatment must be stored according to the instructions specified on the label.

Clinical supplies are to be dispensed only in accordance with the protocol. Technical complaints are to be reported to the respective Novartis CO Quality Assurance.

Medication labels will be in the local language and comply with the legal requirements of each country. They will include storage conditions for the study treatment but no information about the participant except for the medication number.

The investigator must maintain an accurate record of the shipment and dispensing of study treatment in a drug accountability log. Monitoring of drug accountability will be performed by monitors during site visits or remotely and at the completion of the trial. Participants will be asked to return all unused study treatment and packaging at the end of the study or at the time of discontinuation of study treatment.

At the conclusion of the study, and as appropriate during the course of the study, the investigator will return all unused study treatment, packaging, drug labels, and a copy of the completed drug accountability log to the Novartis monitor or to the Novartis address provided in the investigator folder at each site.

6.7.1.2 Handling of additional treatment

Artificial tears will be provided to the participants for use at home between the Screening and Baseline visits. Participants will return artificial tears at the Baseline visit.

6.7.2 Instruction for prescribing and taking study treatment

Participants should take the study treatment at approximately the same time each day, twice-a-day. For example, morning dose at approximately 8 am and evening dose at approximately 8 pm. If a dose is missed and it has been more than six hours from the approximate usual time of dosing, participants should continue with the next scheduled dose.

All kits of study treatment assigned by the IRT will be recorded in the IRT system.

7 Informed consent procedures

Eligible participants may only be included in the study after providing (witnessed, where required by law or regulation), IRB/IEC-approved informed consent.

If applicable, in cases where the participant's representative(s) gives consent (if allowed according to local requirements), the participant must be informed about the study to the extent possible given his/her understanding. If the participant is capable of doing so, he/she must indicate agreement by personally signing and dating the written informed consent document.

Informed consent must be obtained before conducting any study-specific procedures (e.g. all of the procedures described in the protocol). The process of obtaining informed consent must be documented in the participant source documents.

Novartis will provide to investigators in a separate document a proposed informed consent form that complies with the ICH GCP guidelines and regulatory requirements and is considered appropriate for this study. Any changes to the proposed consent form suggested by the investigator must be agreed by Novartis before submission to the IRB/IEC.

Information about common side effects already known about the investigational drug can be found in the Investigator's Brochure (IB). This information will be included in the participant informed consent and should be discussed with the participant during the study as needed. Any new information regarding the safety profile of the investigational drug that is identified between IB updates will be communicated as appropriate, for example, via an investigator notification or an aggregate safety finding. New information might require an update to the informed consent and then must be discussed with the participant.

The following informed consents are included in this study:

- Main study consent
- As applicable, Pregnancy Outcomes Reporting Consent for female Participants.

Women of child bearing potential must be informed that taking the study treatment may involve unknown risks to the fetus if pregnancy were to occur during the study and agree that in order to participate in the study they must adhere to the contraception requirements.

A copy of the approved version of all consent forms must be provided to Novartis after IRB/IEC approval.

Participants might be asked to complete an optional questionnaire to provide feedback on their clinical trial experience.

8 Visit schedule and assessments

The Assessment Schedule ([Table 8-1](#)) lists all of the assessments when they are performed. All data obtained from these assessments must be supported in the participant's source documentation.

Participants should be seen for all visits/assessments as outlined in the assessment schedule ([Table 8-1](#)) or as close to the designated day/time as possible. Missed or rescheduled visits should not lead to automatic discontinuation. Participants who prematurely discontinue the study for any reason should be scheduled for a visit as soon as possible, at which time all of the assessments listed for the final visit will be performed. At this final visit, all dispensed investigational product should be reconciled, and the adverse event and concomitant medications recorded on the CRF.

Assessments assigned to the screening visit can be conducted on separate days as close to each other as possible. Visual acuity and refraction assessments must be performed on the same day.

According to evaluation performed for this study all visits must be performed at site. No evaluation at home is possible with the exception of the [REDACTED], in case of COVID pandemic.

If the COVID-19 pandemic limits or prevents on-site study visits and other study assessments may not be performed, alternative methods of safety monitoring may be implemented. Depending on local regulations, site capabilities and participant's visit status in the study, phone calls or virtual contacts (e.g., teleconsult) can be performed for safety follow-up for the duration of the pandemic, until it is safe for the participant to visit the site again.

If a participant is unable to attend the scheduled baseline visit due to illness, the run-in period could be extended up to 2 weeks from the Screening visit. During this extended run-in period, participants will continue to administer the Sponsor provided artificial tears as directed.

[figure not shown]
[figure not shown]

Table 8-1 Assessment Schedule

Period	Run-in	Treatment					Treatment holiday period									
Visit Name	Screening	Baseline	W2	M1	M2	M3	M4	M5	M6	M7	M8	M9	M10	M11	M12/EOS	
Days	-7	1	14	30	60	90	120	150	180	210	240	270	300	330	360	
Informed consent	X															
Demography	X															
Medical history/current medical conditions	X															
Prior medications	X	X														
Concomitant medications	X	X	X	X	X	X	X	X	X	X	X	X	X	X	X	
Inclusion/Exclusion criteria	X	X														
Vital Signs	X	X				X			X			X			X	
Physical Examination ¹	X														X	
Distance-corrected near visual acuity (letters) ³	X	X	X	X	X	X	X	X	X	X	X	X	X	X	X	

Period	Run-in	Treatment					Treatment holiday period									
Visit Name	Screening	Baseline	W2	M1	M2	M3	M4	M5	M6	M7	M8	M9	M10	M11	M12/EOS	
Days	-7	1	14	30	60	90	120	150	180	210	240	270	300	330	360	
IDEEL blurry vision question ¹	X															
Cycloplegic refraction	X															
Pupil size (non-dilated)	X															
Slit lamp biomicroscopy	X	X	X	X	X	X	X	X	X	X	X	X	X	X	X	
Corneal Staining	X	X	X			X						X			X	
Intraocular Pressure (IOP)	X	X	X	X	X	X	X		X			X			X	
Dilated fundus exam	X					X									X	
Hematology	X					X										
Clinical Chemistry	X					X										
Urinalysis	X					X										
Pregnancy Test (serum)	X															
Pregnancy Test (urine) ¹						X									X	
Adverse Events	X	X	X	X	X	X	X	X	X	X	X	X	X	X	X	
Drug dispensation		X		X	X											
Study completion information															X	
eDiary compliance assessment		X	X	X	X	X										

Period	Run-in	Treatment					Treatment holiday period								
Visit Name	Screening	Baseline	W2	M1	M2	M3	M4	M5	M6	M7	M8	M9	M10	M11	M12/EOS
Days	-7	1	14	30	60	90	120	150	180	210	240	270	300	330	360

^X Assessment to be recorded in the clinical database or received electronically from a vendor

[figure not shown]
¹ Assessment to be recorded in the source documentation only

█ [REDACTED]

³ Duplicate binocular DCNVA assessments will be completed at all visits

█ [REDACTED]

█ [REDACTED]

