Ophthalmic Examination	The following ocular assessments will be performed as per the schedule assessment: 
1. Slit-lamp biomicroscopy include evaluation of the lids/lashes, conjunctiva, cornea (including corneal staining using the grading scale below), anterior chambers aqueous reactions (cells and flare), iris, lens and anterior part of the vitreous body and assessment of phacodonesis in both eyes. Slit-lamp examination will be performed before study treatment and throughout the study. Phacodonesis should be assessed at Screening, and Month 3 visits. The results will be recorded in the source documents only and any clinically significant findings must be documented in the eCRF.2. Intraocular pressure will be assessed in both eyes with Goldmann applanation tonometer or Tonopen. This assessment must be performed after any visual acuity assessments.3. Dilated fundus examination will be performed in both eyes. Any clinically significant findings must be documented in the eCRF.

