8.4.3 Pregnancy and assessments of fertility

All pre-menopausal women who are not surgically sterile will have pregnancy testing. Additional pregnancy testing might be performed if requested by local requirements. A serum pregnancy test is performed at screening and a urine pregnancy test is sufficient at other timepoints. However, a positive urinary pregnancy test needs to be confirmed with a serum pregnancy test.

Medical documentation of oophorectomy, hysterectomy, or tubal ligation must be retained as source documents. Subsequent hormone level assessment to confirm the woman is not of child-bearing potential must also be available as source documentation in the following cases:

1. Surgical bilateral oophorectomy without a hysterectomy
2. Reported 12 months of natural (spontaneous) amenorrhea with an appropriate clinical profile.

In the absence of the above medical documentation, FSH testing is required of any female participant regardless of reported reproductive/menopausal status at screening/baseline.

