9.1.2 Withdrawal of informed consent

Participants may voluntarily withdraw consent to participate in the study for any reason at any time. Withdrawal of consent occurs only when a participant:

- Does not want to participate in the study anymore, and
- Does not want any further visits or assessments and
- Does not want any further study related contacts

In this situation, the investigator should make a reasonable effort (e.g. telephone, e-mail, letter) to understand the primary reason for the participant's decision to withdraw his/her consent and record this information.

Where consent to the use of personal and coded data is not required, participant therefore cannot withdraw consent. They still retain the right to object to the further use of personal data.

Study treatment must be discontinued and no further assessments conducted, and the data that would have been collected at subsequent visits will be considered missing.

[figure not shown]
Further attempts to contact the participant are not allowed unless safety findings require communicating or follow-up.

All efforts should be made to complete the assessments prior to study discontinuation. A final evaluation at the time of the participant's study discontinuation should be made as detailed in the assessment table.

Novartis will continue to retain and use all research results (data) that have already been collected for the study evaluation.

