2.1.1.3 End of study/end of treatment mapping

The *end of study* date (from 'Study disposition' CRF) is the date when a subject completes or discontinues the study. The *end of treatment* date (from 'Treatment disposition' CRF) is the date when a subject completes or discontinues the treatment.

To report data by visit in the outputs, the end of study with early discontinuation will be allocated to Month 12 /End of Study (Month 12/EOS) visit. To be more specific, any visit name equal to "Early Exit Visit" will be allocated to "Month 12/EOS" and analyzed as "Month 12/EOS".

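### Participants who leave the study before Month 3 are sent to the Month 12/EOS assessment list, so they have no scheduled post-dose hematology, chemistry or urinalysis

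*Protocol*

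**What the plan says.** - **Protocol Section 8 (Visit schedule and assessments):** anyone leaving the study early, whatever the cause, is to be given a prompt visit, "at which time all of the assessments listed for the final visit will be performed".
- **Protocol Table 8-1:** the last column is M12/EOS, and there is no separate early-exit column. The rows for hematology, "Clinical Chemistry" and urinalysis are marked at Screening and M3 and nowhere else. In the current table these rows carry no footnote.
- **SAP 2.1.1.3:** "any visit name equal to 'Early Exit Visit' will be allocated to 'Month 12/EOS' and analyzed as 'Month 12/EOS".
- **Protocol 9.1.2 (withdrawal of consent):** "All efforts should be made to complete the assessments prior to study discontinuation". The final evaluation is referred back to the assessment table.
- **Protocol 9.1.1:** participants who stop study treatment are not regarded as withdrawn unless they withdraw consent, and are asked to return for the scheduled assessments where possible. Those who leave the study during the treatment period get a safety call 30 days after their last dose.
- **SAP 2.8.3:** hematology, chemistry and urinalysis results are listed by treatment group, subject and visit/time. No summary is planned.

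**The concern.** The M12/EOS column is built for someone nine months off treatment, for whom omitting blood and urine panels is understandable. The same column also serves as the exit list for someone who leaves during the three months of dosing. Month 3 is the only scheduled post-dose laboratory time point, so a participant who exits before it misses the panels altogether.

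What is at stake is safety review of the individual. Protocol 10.1.1 identifies laboratory adverse events partly by looking for out-of-range values and significant changes from baseline, and neither can be done without a post-dose sample. The participants without one are early leavers, whose reasons for leaving may not be unrelated to treatment. The plan also gives some reason to want these data: the earlier studies used the chloride salt whereas this one uses the tosylate (Section 1.1), and the range extends to 30 mg/mL, above the 13.3 mg/mL equivalent studied before (Section 4.2).

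**Working it through.** There is no stated figure to reproduce for the schedule itself. The check is to read the table by column and then size the group from the plan's drop-out assumption.

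**Step 1. Which list applies at early exit.** Section 8 points to the final visit, the last column of Table 8-1 is M12/EOS, and SAP 2.1.1.3 gives the same mapping. The two documents agree.

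**Step 2. What the columns contain (Table 8-1).**

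| Assessment | Marked at | At M12/EOS? |
|---|---|---|
| Hematology | Screening, M3 | No |
| Clinical chemistry | Screening, M3 | No |
| Urinalysis | Screening, M3 | No |
| Serum pregnancy test | Screening | No |
| Urine pregnancy test | M3, M12/EOS | Yes |
| Dilated fundus exam | Screening, M3, M12/EOS | Yes |

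Vital signs, DCNVA, slit lamp, corneal staining and IOP are marked at both M3 and M12/EOS. Among the visible rows, the tests that M3 has and M12/EOS lacks are the three safety panels.

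**Step 3. Count for a participant leaving between Day 1 and the M3 visit.** Scheduled post-dose panels before M3: none (no marks at Baseline, W2, M1 or M2). At the exit visit: none. Total: 0.

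**Step 4. Whether another section supplies the tests.**
- Section 9.1.1: the 30-day contact is a call, so it yields no sample.
- Section 9.1.2: refers back to the assessment table.
- Section 8.4.2: follows up clinically significant abnormal values, which presupposes that a sample was taken.
- Section 14: allows added safety assessments case by case, without requiring any at exit.

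**Step 5. How many participants.** Inputs are 225 randomized, about 5% drop-out over three months, and 210 as the number required or expected to complete (Protocol Sections 5 and 12.8.1).
- Consistency of the inputs: 210 / 0.95 = 221.05, so 222. The plan's 225 rounds this up to 45 per arm.
- From the rate: 0.05 × 225 = 11.25, about 11, or 11.25 / 5 = 2.25 per arm.
- From the difference: 225 − 210 = 15, or 3 per arm. As a rate this is 15 / 225 = 6.7%, somewhat above the stated 5%.

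Both figures are ceilings. They count every drop-out as a study exit, and some of these participants will not attend an exit visit.

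**The case against.** The strongest reply is that the protocol works to keep people in the study. Section 6.5 has participants who do not tolerate the regimen stop treatment and, if possible, continue to be monitored. Section 9.1.1 does not count them as withdrawn unless they withdraw consent. A reader might infer that someone who stops the drops on Day 45 for an adverse event has no laboratory follow-up. The documents do not support that: such a participant is asked back for the scheduled visits, including M3 and its panels. This part of the reply stands and confines the gap to people who leave the study itself.

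A reader might also infer that early leavers have no post-dose laboratory data of any kind, or that an abnormality could never be found. That is also too strong. M12/EOS includes a urine pregnancy test, which Table 8-4 places among the laboratory evaluations. It applies only to some women ("All pre-menopausal women who are not surgically sterile will have pregnancy testing") and says nothing about hematology or chemistry, but it is a test. Section 14 lets an investigator order further safety assessments, and Section 10.1.1 requires adverse events to be followed to resolution or until judged permanent. What is missing is the routine scheduled panel.

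Nor does the gap clearly extend to phacodonesis. Table 8-2 does say "Phacodonesis should be assessed at Screening, and Month 3 visits", but it also includes that assessment within slit-lamp biomicroscopy, which Table 8-1 marks at every visit.

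Finally, it can be said that the matter is minor: the product is a topical eye drop, the two earlier studies reported no serious adverse events and no discontinuations from the study for an adverse event (Section 4.5), laboratory data are only listed, and no estimand depends on them. All of that bears on priority. It does not explain why a participant attending a required exit visit during the treatment period should miss panels planned for that participant at Month 3.

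**Conclusion.** The point holds in a narrow form. A participant who leaves the study before the Month 3 visit and attends the exit visit has no scheduled post-dose hematology, chemistry or urinalysis, and no other visible provision requires one.

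The size is at most about 11 participants (5% of 225), or 15 (225 minus 210), roughly two or three per arm. The number who could actually be sampled is smaller and the documents do not give it, because those lost to follow-up, or who withdraw consent and decline a final evaluation, provide no sample under any list. The early termination described in the SAP does not enlarge the group: it followed an interim analysis timed for when everyone had completed Month 3 or discontinued before it.

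The consequence is a loss to individual safety review. No efficacy result, power figure or error rate is touched. The conclusion assumes that the final visit means the M12/EOS column, as the SAP mapping indicates, and that the redacted table footnotes do not alter the three laboratory rows, which carry no footnote mark. It is a low-cost improvement worth making, not a flaw that threatens the trial.

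**What to change.** 1. **Protocol Section 8 and a footnote to Table 8-1:** state that an early exit visit before the Month 3 visit includes the M3 hematology, clinical chemistry and urinalysis in addition to the M12/EOS items. Keep the M12/EOS list unchanged for later exits.
2. **SAP 2.1.1.3 and 2.8.3:** list these samples by actual study day. Under the present mapping, a sample taken during the treatment period would be labelled Month 12/EOS and read as if taken nine months off drug.

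The cost is one sentence, one footnote and one SAP line, plus one blood and urine sample from each participant who attends such a visit. That sample was already planned for them at Month 3, and the visit is already required.

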6.3.2 Treatment assignment, randomization

At baseline visit, all eligible participants will be randomized via Interactive Response Technology (IRT) to one of the treatment arms. The investigator or his/her delegate will contact the IRT after confirming that the participant fulfills all the inclusion/exclusion criteria. The IRT will assign a randomization number to the participant, which will be used to link the participant to a treatment arm and will specify a unique medication number for the first package of study treatment to be dispensed to the participant.

The randomization numbers will be generated using the following procedure to ensure that treatment assignment is unbiased and concealed from participants and investigator staff. A participant randomization list will be produced by the IRT provider using a validated system that automates the random assignment of participant numbers to randomization numbers. These randomization numbers are linked to the different treatment arms, which in turn are linked to medication numbers. A separate medication list will be produced by or under the responsibility of Novartis Global Clinical Supply (GCS) using a validated system that automates the random assignment of medication numbers to packs containing the study treatment.

Randomization will be stratified based on binocular DCNVA (0.5 logMAR or less; 0.52 logMAR or more) and age (45 to 50 years and 51 to 55 years) at baseline, and region.

Participants will be randomized 1:1:1:1:1 within each stratum to either treatment arm. The randomization scheme for participants will be reviewed and approved by a member of the Randomization Office.

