8.4.2 Laboratory evaluations

A central laboratory will be used for analysis of all specimens collected.

The central laboratory will flag laboratory values falling outside of the normal ranges on the central laboratory reports. Investigators are responsible for reviewing these abnormal values for clinical significance, signing the laboratory reports to indicate their review, and reporting values considered clinically significant in the appropriate eCRF page.

Clinically significant abnormalities at screening must be recorded as medical history/current medical conditions.

Any clinically significant abnormal laboratory value should be evaluated and followed-up by the investigator until normal or a cause for the abnormality is determined. All abnormal lab results must be evaluated for criteria defining an adverse event and reported as such if the criteria are met.

Table 8-4 Laboratory evaluations

Test Category	Test Name
Hematology	Hemoglobin, platelets, white blood cells, differential (basophils, eosinophils, lymphocytes, monocytes, neutrophils, and other)
Chemistry	Albumin, alkaline phosphatase, serum alanine aminotransferase, serum aspartate aminotransferase, lactate dehydrogenase, calcium, magnesium, phosphorus, sodium, potassium, creatinine, direct bilirubin, total bilirubin, urea, uric acid, amylase, lipase, glucose (non-fasting), and glycated hemoglobin (HbA1c).
Urinalysis	
Macroscopic (Dipstick) panel - color, bilirubin, blood, glucose, ketones, leukocyte esterase, nitrite, pH, protein, specific gravity, and urobilinogen
 
Microscopic panel - red blood cells, white blood cells, casts, crystals, bacteria and epithelial cells. Microscopic analysis is only required if any parameter of the macroscopic panel is abnormal.

Pregnancy Test	serum pregnancy test at screening/ urine pregnancy test will be done at the other required time points.

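### Table 8-1 schedules no pregnancy test between Screening and Month 3; urine tests at M1 and M2 before dispensing would be a low-priority safety improvement

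*Protocol*

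**What the plan says.** Table 8-1 has two pregnancy-test rows. The serum row is marked at Screening (Day -7) only. The row "Pregnancy Test (urine" is marked at M3 (Day 90) and M12/EOS (Day 360) only. Its one footnote says that the result goes in the source documents, so redaction does not explain the empty cells at Baseline, W2, M1 and M2. Drug dispensation is marked at Baseline, M1 and M2.

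The text adds no timepoint. Table 8-4 says that a "urine pregnancy test will be done at the other required time points" without naming them. Section 8.4.3 says "Additional pregnancy testing might be performed if requested by local requirements", and that "a positive urinary pregnancy test needs to be confirmed with a serum pregnancy test".

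The row "Inclusion/Exclusion criteria" is marked at Screening and again at Baseline. Under Section 6.3.2 the investigator or delegate "will contact the IRT after confirming that the participant fulfills all the inclusion/exclusion criteria". Exclusion 30 bars pregnant women. Sections 9.1.1 and 10.1.4 require treatment to stop if a participant becomes pregnant. Section 4.5 records that effects on pregnancy are unstudied and that no safety concern is expected.

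**The concern.** The protocol has a stop rule for pregnancy, but no scheduled test supports that rule while most of the dosing lies ahead. The first scheduled test after Screening comes at about the planned end of dosing. Before then a pregnancy would surface only if the participant reports it, if the non-directive questioning at visits (10.1.1) or an incidental finding reveals it, or if local rules require an extra test.

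What is at stake is avoidable fetal exposure to a drug whose reproductive effects are unstudied, in a condition that Section 4.3 calls non-serious. How often an unrecognised pregnancy would be re-supplied depends on when it begins: twice if before M1, once if between M1 and M2, and not at all if after M2.

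**Working it through.** The documents state no test interval, so there is no figure to reproduce.

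**Intervals.** Table 8-1 gives the nominal days: Screening -7, Baseline 1, M1 30, M2 60, M3 90. SAP 2.1.1.2 has no Day 0, so Day -7 is 7 days before Day 1. Section 8 allows the run-in to reach 2 weeks in case of illness.
- Screening to M3: 7 + (90 - 1) = 96 days; extended run-in: 14 + 89 = 103 days.
- On drug: 90 - 1 = 89 days.
- With tests added at M1 and M2, on-drug intervals are 30 - 1 = 29, 60 - 30 = 30 and 90 - 60 = 30 days. Counted from Screening, the first interval is 7 + 29 = 36 days (14 + 29 = 43 if extended). A Baseline test would split it.
- Dosing still to be withheld after a positive: 90 - 30 = 60 days at M1, 90 - 60 = 30 days at M2.

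**Number of women tested (assumed).** The documents do not give the share of women or of child-bearing potential. Assume 40% to 60% women, of whom 20% to 60% are of child-bearing potential:
- 225 x 0.4 x 0.2 = 18; 225 x 0.6 x 0.6 = 81.

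**Pregnancies during 90 days of dosing.** Exclusion 31 gives a failure rate below 1% in its item on hormonal methods. Reading that as annual, and applying it to all methods, is an assumption.
- At 1% per year: 18 x 0.01 x 90/365 = 0.044; 81 x 0.01 x 90/365 = 0.20.
- At 0.1% with 18 women: 0.004. At 5% with 81 women: 1.0.
- Tests at M1 and M2 can find only pregnancies that begin before Day 60, at most 60/90 = two thirds: 0.044 x 2/3 = 0.03 to 0.20 x 2/3 = 0.13 at 1% per year. Any detection lag lowers this.

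**Burden of M1 and M2 tests.**
- Strips: 2 x 18 = 36 to 2 x 81 = 162.
- False positives at an assumed specificity of 99.9% to 99%: 36 x 0.001 = 0.04 to 162 x 0.01 = 1.6 in the whole trial.
- Length of a hold: Section 8.4.2 says "A central laboratory will be used for analysis of all specimens collected" but gives no turnaround. Assuming 2 to 7 days, a hold omits 4 to 14 of 2 x 90 = 180 dosing times (2% to 8%) for that woman.

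**The case against.** The strongest reply is that the plan is already layered and proportionate. It has a serum test at Screening, mandatory contraception during dosing with three months' stability on the pill, non-entry or non-continuation if compliance is in doubt (4.5), and counselling on unknown fetal risk (Section 7). Where reproductive status is undocumented, "FSH testing is required of any female participant regardless of reported reproductive/menopausal status at screening/baseline". Participants are aged 45 to 55, and the sponsor expects no safety concern. Nothing in the documents requires monthly testing. All of this stands as a reason for low priority. These measures make pregnancy less likely, but none of them detects one.

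The reply on cost also has force. False positives would run from about level with early detections (0.036 against 0.030) to about 12 to 1 (1.62 against 0.133). Because drug is dispensed at the clinic (6.7), a withheld kit may mean a return visit.

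A reader might infer more than the documents support:
- **That sections contradict each other, or that the Baseline eligibility check is breached.** They do not: no passage requires a test at Baseline, and a serum test was done 7 to 14 days before.
- **That no scheduled test could ever trigger the stop rule during dosing.** That is too absolute. Visits fall as near as possible to the nominal day, so an M3 visit could precede the last few doses.
- **That the whole 96 to 103 days is exposure.** Only 89 days are on drug.

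**Conclusion.** The gap is real and is correctly read from Table 8-1: 89 on-drug days, and 96 to 103 days in all, without a scheduled pregnancy test. It merits consideration as an inexpensive safety improvement and no more than that. The day counts rest on nominal visit days. The expected benefit, 0.03 to 0.13 pregnancies open to early detection in the whole trial, rests on the assumed shares of women and the assumed 1% per year. Over assumed rates of 0.1% to 5% the same two thirds gives 0.003 to 0.67.

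It does not affect the primary endpoint, power or error rate. The SAP records the Month 3 interim analysis as completed on 24 August 2022 (Section 1) and the program as discontinued for lack of efficacy (Section 1.1). Nothing can change for these participants.

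**What to change.** In any later protocol that reuses this schedule:
- **Table 8-1, urine row:** add X at M1 and M2, with Baseline optional. Footnote: women of child-bearing potential only; done before dispensing at on-site visits; after a positive result, dispensing and dosing are held until the serum confirmation that Section 8.4.3 already requires.
- **Section 6.5:** it permits no interruptions, so add this hold as the one exception.
- **Data handling:** state that a temporary hold is not an intercurrent event and its data are kept, since SAP 2.5.3.1 does not list it, and that a confirmed pregnancy that stops treatment is ICE 2 (discontinuation for other reasons).
- **Remote supply under COVID-19 (6.7):** the before-dispensing test cannot be applied there unless Section 8 is amended. That section bars evaluation at home apart from one redacted exception.

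The longest untested on-drug interval falls from 89 days to about 30. The cost is 36 to 162 strips under the assumed shares (54 to 243 with Baseline), at visits already attended. Each false positive adds a short dosing hold and possibly a return visit to collect drug.
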